#### 4.5 Duration of Follow-Up

Patients will be followed per usual protocol for primary hip and knee arthroplasty patients, including inpatient stay (1-4 days on average) and a two-week clinic follow-up appointment. After patient completes the AUA Symptom Index and the Toxicity Assessment Survey and submits their opioid pain medication log at the two-week follow-up appointment, **active** participation in the study will conclude, however we will monitor their medical records for 30 post operatively

During the inpatient stay, patients will continue to take tamsulosin or placebo until the 7-capsule regimen is complete or until one of the end-of-protocol-therapy criteria listed in section 5.5 is met. If the patient goes on to treatment failure, he may be discharged on tamsulosin at the discretion of his physician. It will be noted if a patient is discharged on tamsulosin and appropriate follow-up will be arranged with either the patient's primary care physician or urologist.

#### 4.6 Removal of Patients from Protocol Therapy

Patients will be removed from therapy when any of the criteria listed in Section 5.5 apply. The Principal Investigator will be notified, and the reason for therapy removal and the date the patient was removed will be documented on the Case Report Form. The patient should be followed-up per protocol.

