**STUDY SCHEMA**

**STUDY SUMMARY**

Title	Prospective, randomized, double-blind, placebo-controlled trial of prophylactic tamsulosin for postoperative urinary retention in primary total hip and knee arthroplasty patients
Short Title	Prophylactic tamsulosin for postoperative urinary retention in hip and knee arthroplasty
Phase	Phase 3
Methodology	Prospective, randomized, double-blind, placebo-controlled
Study Duration	1.5 - 3 years until a prior calculated sample size reached (see above)
Study Center(s)	Single-center
Objectives	Determine if prophylactic tamsulosin given beginning five days prior to surgery through post-op day one reduces the incidence of postoperative urinary retention in total hip and knee arthroplasty patients
Number of Subjects	456 screened with a 50% accrual rate (182 total subjects needed with 20% dropout for a total of 228 patients enrolled)

Control Group	91 patients undergoing primary total hip or knee arthroplasty who are on an $\alpha$ 1-adrenoceptor blocker at the time of surgery
Diagnosis and Main Inclusion Criteria	Postoperative urinary retention in primary total knee and hip arthroplasty patients
Study Product(s), Dose, Route, Regimen	Tamsulosin 0.4 mg p.o. daily
Duration of administration	Five days prior to operation until post-op day one (seven days total)
Reference therapy	Placebo
Statistical Methodology	Two-tailed t-test for primary outcome, (80% power, $\alpha = 0.05$ )

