#### 4.7 Patient Replacement

Patients will not be required to be replaced as the study will continue until the minimal sample size, as determined by a prior sample size calculation, is reached.

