## 5.5 Removal of Subjects from Study/Study Treatment

- 5.5.1 Patient voluntarily withdraws from treatment (follow-up permitted)
- 5.5.2 Patient withdraws consent (termination of treatment and follow-up)
- 5.5.3 Patient is unable to comply with protocol requirements
- 5.5.4 Patient experiences toxicity that makes continuation in the protocol unsafe
- 5.5.5 Treating physician judges continuation in the study would not be in the patient's best interest

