**10.2 Sample Size and Accrual**

POUR occurs in approximately 40% of patients following primary total hip or knee arthroplasty. Risk factors for POUR include male sex, total hip arthroplasty, intrathecal morphine and epidural anesthesia. A sample size of 91 in each arm (tamsulosin versus placebo) is needed with continuity correction if a reduction of 50% (or a POUR incidence of 20%) is to be detected with a power of 80% at a significance level of  $\alpha < 0.05$ . 114 patients are need in each arm assuming an accrual rate of 80% for a total of 228 patients.

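### Stopping capsules is not separated from leaving the study, and no efficacy set by randomised arm is defined, so men who stop early can be dropped or regrouped although their POUR outcome is obtainable

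*Combined protocol and SAP*

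**What the plan says.** **Removal and follow-up.** Section 4.6: "Patients will be removed from therapy when any of the criteria listed in Section 5.5 apply". It then adds, with no exception: "The patient should be followed-up per protocol". Section 5.5 is one list under a heading that covers both the study and the study treatment.

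- 5.5.1 (voluntary withdrawal from treatment) permits follow-up.
- 5.5.2 ends it: "Patient withdraws consent (termination of treatment and follow-up".
- 5.5.3 reads "Patient is unable to comply with protocol requirements". Neither it, nor 5.5.4 (toxicity), nor 5.5.5 (physician's judgement) mentions follow-up.

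Section 4.5 points to 5.5 for the criteria that end protocol therapy. Those criteria are in 4.4, and that list differs: it includes completing the capsules, a monitoring catheter and death.

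**Numbers.** The Study Summary gives "182 total subjects needed with 20% dropout for a total of 228 patients enrolled". Section 10.2 gives 91 per arm, raised to 114, and describes the allowance as an 80% accrual rate. Section 4.7 says replacement is not required because "the study will continue until the minimal sample size, as determined by a prior sample size calculation, is reached".

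**Analysis.** Section 6.1 defines a population for safety only (at least one dose). For the primary outcome, section 10.3 contrasts men who are and are not taking tamsulosin when they have surgery. Section 2.3 takes POUR from the hospital's electronic record. An asymptomatic man who needs no intermittent catheterisation and has no residual volume recorded counts as free of POUR.

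**The concern.** Six of the seven capsules are due by the morning of surgery, and the Foley catheter comes out on the morning of postoperative day one (4.1.3). A man can therefore stop capsules well before his outcome is observed. If he still has surgery and has not withdrawn consent, the record will show whether he developed POUR.

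Nothing in the plan ensures that he is counted in the arm to which he was randomised. Staff could read 5.5.3 to 5.5.5 as taking him off study. An analyst following 10.3 literally could place a tamsulosin-arm man who stopped before surgery with the men not taking the drug. An analyst aiming for 182 evaluable men could leave him out.

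Dizziness, postural hypotension and syncope appear in 7.1.4 as alpha-blocker-associated, so stopping could plausibly differ by arm. The protection of randomisation would then be lost although the data to keep it are available.

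**Working it through.** **1. Reproduce the plan's sample size.** Inputs from section 10.2: "POUR occurs in approximately 40% of patients following primary total hip or knee arthroplasty" and "if a reduction of 50% (or a POUR incidence of 20%) is to be detected", so p1 = 0.40, p2 = 0.20, d = 0.20, p̄ = 0.30. Two-sided α is 0.05 and power 80%.

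- Uncorrected: n0 = [1.96√(2·0.30·0.70) + 0.842√(0.24 + 0.16)]² / 0.20² = 81.2.
- Continuity-corrected: n = (n0/4)[1 + √(1 + 4/(n0·d))]² = 90.9, so 91 per arm.
- Dropout: 91/0.80 = 113.75, so 114 per arm and 228 in total.

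All match. The allowance leaves 228 − 182 = 46 men outside the number needed, or 23 per arm.

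**2. Passages side by side.**

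| Criterion | Follow-up under 5.5 | Follow-up under 4.6 | Result |
|---|---|---|---|
| 5.5.1 | permitted | yes | consistent |
| 5.5.2 | ended | yes | contradiction |
| 5.5.3 to 5.5.5 | not stated | yes | unclear whether treatment or study ends |

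Section 4.7 does not say whether its minimum is 182 or 228, or whether it counts enrolled or evaluable men.

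**3. Illustrate the effect of dropping men.** Assumptions, none of them from the documents except the 40%: no true effect, the same share f removed in each arm, placebo removals unrelated to POUR, and POUR of r among removed tamsulosin men. The retained tamsulosin rate is (0.40 − f·r)/(1 − f). For f = 0.20 and r = 0.60 it is (0.40 − 0.12)/0.80 = 35.0%, a false benefit of 5.0 points. Exact binomial enumeration of the uncorrected chi-square test, held at 91 v 91 throughout, gives the chance of p<0.05:

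| Removed per arm | r = 50% | r = 60% | r = 70% |
|---|---|---|---|
| 5% | 5.1% | 5.3% | 5.7% |
| 10% | 5.4% | 6.3% | 7.7% |
| 20% | 6.6% | 11.0% | 18.8% |

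With removal unrelated to POUR it is 5.1%. If removed tamsulosin men had less POUR, the bias would reverse: at f = 0.20 and r = 0.30 the retained rate is (0.40 − 0.06)/0.80 = 42.5%, which makes the drug look worse. The table covers dropping men; the effect of regrouping them is not quantified.

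**4. Cost of keeping everyone.** If a share s of tamsulosin men stop and revert to 40% risk, p2 = 0.20(1 − s) + 0.40s. Power is Φ{[d√n0 − 1.96√(2p̄(1 − p̄))] / √(p1(1 − p1) + p2(1 − p2))}, where n0 is the uncorrected size equivalent to 114 per arm.

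- s = 0: p2 = 0.20, n0 = 104.2, power 88.9%.
- s = 10%: p2 = 0.22, n0 = 103.2, power 80.3%.
- s = 20%: p2 = 0.24, n0 = 101.8, power 69.0% (80% would need 145 per arm).

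These figures assume that all 228 men have surgery and a usable record. At 91 per arm and s = 0, power is 80.0%.

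**The case against.** The strongest reply is that little here is a true contradiction. Section 4.6 concerns removal from therapy and asks for follow-up, which can be read as settling 5.5.3 to 5.5.5. It agrees with 5.5.1, and the specific wording of 5.5.2 naturally limits the general sentence. This largely stands: the direct conflict is confined to 5.5.2, and the rest is ambiguity created by the heading of 5.5.

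A reader might go further and infer several things that the documents do not support:

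- **That 4.7 refills the places of removed men.** It says replacement is not required. Refilling is only one reading of recruiting to an undefined minimum.
- **That removed men are excluded from the POUR analysis.** No section orders this, and 4.6 leans the other way. The exposure comes from the missing efficacy set and the wording of 10.3.
- **That the plan expects 46 men to be lost through stopping capsules.** The 20% is general dropout, and 10.2 calls it accrual.
- **That the bias favours tamsulosin.** Nothing in the documents links dizziness or missed doses to POUR risk.
- **That the outcome is already recorded at removal.** A man who stops before surgery has no outcome yet; it becomes obtainable if he goes on to surgery with consent in place.

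It is also fair to say that 20% removal is an extreme case. Section 7.1.4 lists drug-related discontinuation of 26 (5%), and at 5% the inflation is negligible under these assumptions. The wording in 10.3 may also be loose shorthand for the two arms named in 10.2. Even so, it is the only definition of the primary comparison, and taken literally it groups men by exposure.

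**Conclusion.** The concern holds as a gap in definitions that should be closed. One explicit contradiction (4.6 against 5.5.2), three criteria of unclear scope, a mismatched cross-reference (4.5 to 5.5 instead of 4.4), an undefined recruitment minimum and no efficacy set by randomised arm together allow men with an obtainable outcome to be dropped or regrouped.

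The sample-size arithmetic is sound. The size of any bias depends on assumed POUR rates among removed men. It ranges from negligible at 5% removal to a false-positive rate of 18.8% in the worst case shown, where 20% are removed and 70% of the removed tamsulosin men have POUR. It could run either way. These figures show what the wording permits and do not predict what will happen.

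**What to change.** 1. **Sections 4.4, 4.5, 4.6 and 5.5:** reconcile the lists so that stopping capsules is distinct from ending data collection. Only withdrawal of consent ends data collection, with data to that date kept. Exempt 5.5.2 from the follow-up sentence in 4.6. The 4.4 list should not be carried over whole, because it includes completing the regimen and a withdrawal item that does not separate treatment from consent. This concerns data handling, not when treatment should stop.
2. **Sections 4.7 and 10.2:** state that enrolment ends at 228 randomised, and that the 20% allowance covers only men with no surgery or no permitted record.
3. **Section 10.3:** compare randomised arms, including every randomised man who has surgery and has not withdrawn consent for record review, whether or not he finished the capsules. Keep a completer analysis as a sensitivity analysis.
4. **Sections 2.3 and 4.4 item 5:** state how a man with an indwelling monitoring catheter is scored, so that the default for an unrecorded residual volume does not count him as free of POUR.

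The changes are to wording only, since the inpatient record is already the data source. The cost to state openly is dilution of the effect by men who stop early, with the loss of power shown in the working.

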#### 4.7 Patient Replacement

Patients will not be required to be replaced as the study will continue until the minimal sample size, as determined by a prior sample size calculation, is reached.

### 5. PROCEDURES

#### 5.1 Screening/Baseline Procedures

Assessments performed for clinical indications (not exclusively to determine study eligibility) may be used for baseline values even if the assessments were done before informed consent was obtained. All screening procedures must be performed within 30 days prior to registration unless otherwise stated. The screening procedures include:

- 5.1.1 *Informed consent*
- 5.1.2 *Medical history*  
Complete medical and surgical history, history of urinary retention, benign prostatic hypertrophy, urogenital procedures
- 5.1.3 *Demographics*  
Age, gender, race, ethnicity
- 5.1.4 *Review of subject eligibility criteria*
- 5.1.5 *Review of previous and concomitant medications*
- 5.1.6 *Physical exam including vital signs, height and weight (Standard of Care)*  
Vital signs (temperature, pulse, respirations, blood pressure), height, weight
- 5.1.7 *Adverse event and efficacy assessment*  
Baseline adverse events will be assessed. Efficacy will be assessed periodically as well. Adverse events and efficacy will be considered in continuation of the study at enrollment intervals (See Section 5.4). See Section 7 for adverse event monitoring and reporting.
- 5.1.8 *Hematology-(Standard of Care)*  
CBC with differential
- 5.1.9 *Serum chemistries (Standard of Care)*  
Basic metabolic panel (BMP) to include: BUN, creatinine, electrolytes (sodium, potassium, calcium, chloride, bicarbonate), and glucose

## **5.2 Procedures During Treatment**

### **5.2.1 Preoperative**

- Physical exam, vital signs (Standard of Care)
- Hematology (Standard of Care)
- Serum chemistries (Standard of Care)
- Completion of the AUA Symptom Index by the patient
- Completion of the Toxicity Assessment Survey by the patient
- Patient to be given seven capsules of 0.4 mg tamsulosin, with one to be taken daily for the five days before surgery, one on the morning of surgery, and one on the day after surgery. Pills should be administered approximately one half hour following the same meal each day.

### **5.2.2 Postoperative**

- Tamsulosin/placebo taken on postoperative day one
- Completion of the Toxicity Assessment Survey by the patient on post-op day one

**5.2.3 Post-discharge**

[figure not shown]
Patients that go on to treatment failure will be discharged with a plan of care dictated by urology (if consulted), or the primary treatment team, which may include Foley catheter placement, tamsulosin, intermittent straight catheterization, outpatient follow-up with urologist or primary care physician, or some combination of the previously mentioned treatment options.

**5.3 Follow-up Procedures**

Completion of AUA Symptom Index, Toxicity Assessment Survey, and opioid pain medication log by the patient.

**5.4 Time and Events Table**

Event	Pre-operative	Inpatient Stay	2-wk Follow-up
Informed Consent	X		
History and PE	X		X
Performance Status	X		
Toxicity Evaluation	X	X	X
AUA retention score	X		X
Opioid Pain Medication log			X

## 5.5 Removal of Subjects from Study/Study Treatment

- 5.5.1 Patient voluntarily withdraws from treatment (follow-up permitted)
- 5.5.2 Patient withdraws consent (termination of treatment and follow-up)
- 5.5.3 Patient is unable to comply with protocol requirements
- 5.5.4 Patient experiences toxicity that makes continuation in the protocol unsafe
- 5.5.5 Treating physician judges continuation in the study would not be in the patient's best interest

## 6.0 Response Criteria

### 6.1 Safety/Tolerability

Analyses will be performed for all patients having received at least one dose of study drug.

## 7.0 ADVERSE EVENTS

### 7.1 Experimental Therapy

- 7.1.1 *Contraindications*  
History of allergy, sulfa allergy potential for cross sensitivity, poor cyp2d6 metabolizers

7.1.2 *Special Warnings and Precautions for Use*

Floppy iris syndrome in patients undergoing cataract surgery while on Flomax

7.1.3 *Interaction with other medications (per Epocrates):*

Amiodarone, dronedarone, boceprevir, chloramphenicol, clarithromycin, cobicistat, conivaptan, cyclosporine, delavirdine, doxazosin, fluvoxamine, fosamprenavir, imatinib, itraconazole, ketoconazole, lopinavir/ritonavir, nefazodone, nelfinavir, posaconazole, prazosin, rifampin/isoniazid, rifampin/isoniazid/pyrazinamide, ritonavir, telaprevir, telithromycin, terazosin, tipranavir, voriconazole

7.1.4 *Adverse Reactions*

	All	Drug related
Any	390 (76)	132 (26)
$\alpha_1$ -adrenoceptor blocker-associated		
Dizziness	44 (8.5)	30 (5.8)
Abnormal ejaculation	25 (4.9)	22 (4.3)
Headache	24 (4.7)	7 (1.4)
Asthenia	20 (3.9)	10 (1.9)
Rhinitis	18 (3.5)	3 (0.6)
Postural hypotension	15 (2.9)	14 (2.7)

Palpitation	14 (2.7)	7 (1.4)
Dry mouth	8 (1.6)	6 (1.2)
Syncope	5 (1.0)	0
Somnolence	4 (0.8)	2 (0.4)
Other		
Impotence	28 (5.4)	15 (2.9)
Decreased libido	6 (1.2)	4 (0.8)
Urinary retention	23 (4.5)	1 (0.2)
Discontinued treatment	86 (217)	26(5)

Others: allergic reaction, angioedema, Steven Johnson syndrome, arrhythmia, priapism (10)

## 7.2 Adverse Event Monitoring

A study coordinator will monitor for AEs with the use of the patient surveys, at the 2-week follow-up appointment, and with a chart review following the 30-day end-of-study-treatment timepoint. Adverse events will be reported in compliance with the IRB standard reporting guidelines. Additionally, certain adverse events must be reported in an expedited manner to allow for optimal monitoring of patient safety and care. See steps 7.4 and 7.5 for requirements for expedited reporting.

All patients experiencing an adverse event, regardless of its relationship to study drug/device, will be monitored until:

- the adverse event resolves or the symptoms or signs that constitute the adverse event return to baseline,
- any abnormal laboratory values have returned to baseline,
- there is a satisfactory explanation other than the study drug for the changes observed, or
- death.

### 7.3 Definitions

#### 7.3.1 Definition of Adverse Event

An adverse event (AE) is any untoward medical occurrence in a patient receiving study treatment which does not necessarily have a causal relationship with this treatment. An AE can therefore be any unfavorable and unintended sign (including an abnormal laboratory finding), symptom, or disease temporally associated with the use of an experimental intervention, whether or not related to the intervention.

#### 7.3.2 Severity of Adverse Events

The severity of an AE is graded as follows:

Mild (grade 1): the event causes discomfort without disruption of normal daily activities.

Moderate (grade 2): the event causes discomfort that affects normal daily activities.

Severe (grade 3): the event makes the patient unable to perform normal daily activities or significantly affects his/her clinical status.

Life-threatening (grade 4): the patient was at risk of death at the time of the event.

Fatal (grade 5): the event caused death.

#### 7.3.3 Serious Adverse Events

A serious adverse event is defined in regulatory terminology as any untoward medical occurrence that:

##### 7.3.3.1 *results in death,*

If death results from (progression of) the disease, the disease should be reported as event (SAE) itself.

##### 7.3.3.2 *is life-threatening,*

The patient was at risk of death at the time of the event; it does not refer to an event that hypothetically might have caused death if it were more severe.

##### 7.3.3.3 *requires in-patient hospitalization or prolongation of existing hospitalization for ≥ 24 hours,*

##### 7.3.3.4 *results in persistent or significant disability or incapacity,*

7.3.3.5 *is a congenital anomaly/birth defect, or*

7.3.3.6 *is an important medical event.*

Any event that does not meet the above criteria, but that in the judgment of the investigator jeopardizes the patient, may be considered for reporting as a serious adverse event. The event may require medical or surgical intervention to prevent one of the outcomes listed in the definition of “serious adverse event”.

For example: allergic bronchospasm requiring intensive treatment in an emergency room or at home, convulsions that may not result in hospitalization, or development of drug abuse or drug dependency.

#### 7.4 Steps to Determine if an Adverse Event Requires Expedited Reporting

Step 1: Identify the type of adverse event.

Step 2: Grade the adverse event.

Step 3: Determine whether the adverse event is related to the protocol therapy.

Attribution categories are as follows:

- Definite – The AE *is clearly related* to the study treatment.
- Probable – The AE *is likely related* to the study treatment.
- Possible – The AE *may be related* to the study treatment.
- Unrelated – The AE *is clearly NOT related* to the study treatment.

Note: This includes all events that occur within 30 days of the last dose of protocol treatment. Any event that occurs more than 30 days after the last dose of treatment and is attributed (possibly, probably, or definitely) to the agent(s) must also be reported accordingly.

Step 4: Determine the prior experience of the adverse event.

Expected events are those that have been previously identified as resulting from administration of the agent. An adverse event is considered unexpected, for expedited reporting purposes only, when either the type of event or the severity of the event is not listed in:

- the current known adverse events listed in the Agent Information Section of this protocol,
- the drug package insert, or
- the current Investigator’s Brochure

#### 7.5 Reporting Requirements for Adverse Events

All AEs will be reported in adherence to IRB standard reporting guidelines.

7.5.1 Follow expedited reporting procedures when the AE meets any of the following criteria:

1. Any serious event (injuries, side effects, deaths or other problems), which, in the opinion of the Principal Investigator, was unanticipated, involved risk to subjects or others, and was possibly related to the research procedures
2. Any serious accidental or unintentional change to the IRB-approved protocol that alters the level of risk
3. Any deviation from the protocol taken without prior IRB review to eliminate apparent immediate hazard to a research subject

4. Any new information (e.g., publication, safety monitoring report), interim result, or other finding that indicates an unexpected change to the risk/benefit ratio for the research
5. Any breach in confidentiality that may involve risk to the subject or others
6. Any complaint of a subject that indicates an unanticipated risk, or that cannot be resolved by the Principal Investigator

